5.1. General Principles

Descriptive summary statistics will be presented for all primary, secondary, and exploratory endpoints collected by visits and treatment group per schedule of assessment. Unless otherwise specified, for continuous endpoints, the summary statistics will generally include number of participants with data, mean, standard deviation, median, first and third quantiles and range. For categorical endpoints, the summary statistics will generally include number of participants with data, frequency counts and the percentage of those with data in each category. Analyses will be performed on the data from Part 1 alone.

The statistical software, SAS® Version 9.4 or above, will be used for all summaries and statistical analyses.

5.2. Participant Accountability

The summaries will be presented by treatment assignment (80 mg, 10 mg, or placebo).

The number (and percentage) of participants screened, Number of subjects who run-in; randomized, randomized and dosed; completed the treatment; discontinued treatment and the reasons for discontinuation; completed the study and the reasons for withdrawal will be summarized in a table.

A listing of participants who discontinued treatment/withdrew from Part 1 and the associated reasons for discontinuation/withdrawal will be presented.

The number (and percentage) of participants by analysis population will be summarized.

5.3. Demographic and Baseline Characteristics

Summaries of demographic and baseline characteristic data will be summarized by treatment group for the ITT population.

Demographic data, including age (years), age category (<65, >=65 years), sex, ethnicity, race, height, weight, and BMI will be summarized by treatment group and overall.

Baseline characteristics, including diabetic type (type 1, type 2), standard of care medication for DPNP (duloxetine, pregabalin/gabapentin), the duration since DPNP diagnosis, duration of diabetes diagnosis since first dosing (randomization phase), baseline HbA1C, baseline glucose, baseline NPRS score, baseline NPRS category (<7, >=7), baseline DSIS Score, baseline DSIS category (<7, >=7) will be summarized by treatment group and overall.

The duration from DPNP onset and duration of diabetes diagnosis since first randomized dose of study drug will be derived relative to date of DPNP diagnosis and date of diabetes diagnosis.

Medical history will be coded using the Medical Dictionary for Regulatory Activities (MedDRA v24 or higher). A summary of medical history by system organ class and preferred term will also be provided for the safety population. A listing of medical history will be generated.

5.4. Protocol Deviations

Protocol deviations identified will be captured in a protocol deviation log. All protocol deviations are listed and a summary of major protocol deviation by treatment group will be also provided. Protocol deviations may include excluded medications, patients entering the study despite not satisfying all entry criteria, patients receiving wrong treatment or incorrect dose, or other major protocol deviations.

5.5. Study Treatment Exposure

The duration of study drug exposure will be based on the number of days on treatment from the first randomized dose of study drug until the last randomized dose of study drug (last dose – first dose + 1). The first dose should be administrated in clinic and recorded on the Day 1 dosing form. The last dose should be recorded on the end of treatment form.

The number and percentage of subjects in each of the following cumulative duration of exposure categories will be summarized weekly up to Week 12. In addition, days of exposure to the study drug will be summarized as a continuous variable with summary statistics by treatment group and overall.

5.6. Study Compliance

Treatment compliance during the treatment period will be assessed based on the capsules dispensed and returned as recorded in the eCRF.

Total number of doses dispensed, and total dose (mg) dispensed is calculated from total number of kit (bottle) recorded on the Study Drug Dispensation eCRF. One dose requires a capsule from 3 bottles. Total number of doses received is calculated from information on the eCRF of Study Drug Return and Study Drug Dispensation, as the (total number of doses dispensed – total number of doses returned). If a kit is not returned but the patient had a subsequent dispensation, then the non-returned kit is assumed to have been taken in full. However, if a kit is not returned and no kit is subsequently dispensed, then the non-returned kit is assumed to not have been taken. Study drug compliance (%) is calculated as $100 \times total$ number of doses received / total number of exposure days of the randomized study drug.

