## 5.6. Unscheduled Visits

Unscheduled visits may be performed at any time and for any reason, including those not specifically mentioned in this section, as deemed necessary by the Investigator.

Unscheduled visits conducted for the following reasons should include collection of AEs, clinical chemistry, hematology, concomitant medication collection, and vital signs:

- Management of an AE or SAE;
- Performance of additional laboratory tests for clinically abnormal laboratory test values or to confirm a possible pregnancy;
- Subject safety evaluation.

Unscheduled visits conducted for the following reasons do not require additional assessments unless deemed necessary by the Investigator:

- Study drug dispensation;
- Any operational need that would require the subject to return to the site between scheduled visits.

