# 7.3. Study Drug Packaging and Labeling

The study drug will be supplied in tamper-evident kits containing high-density polyethylene bottles. Each bottle will utilize foil induction-seal liners and a child-resistant closure. In Part 1, each bottle of study drug will contain 30 capsules of 10 mg or 40 mg strength RTA 901 or the matching placebo capsules. In Part 2, each bottle of study drug will contain 30 capsules of RTA 901 or matching placebo capsules, depending on the doses of RTA 901 recommended by the DSC (see Section 3.6).

In Part 1, the study drug kits will contain a combination of bottles, each containing active or placebo capsules in varying strengths to make up each dosing regimen. Table 9 shows the combination of bottles that will be used to comprise the dose for each treatment arm, while maintaining the study blind in Part 1. Kit configurations for Part 2 will depend on the doses recommended by the DSC. As in Part 1, the kits for each treatment arm will contain the same

number of bottles and the same configuration of capsule sizes necessary to maintain the study blind.

**Table 9:** Study Drug Kit Configurations – Part 1

Treatment Arm	Bottles of 10 mg Size #4 RTA 901	Bottles of Size #4 Placebo	Bottles of 40 mg Size #0 RTA 901	Bottles of Size #0 Placebo
Placebo	0	1	0	2
RTA 901 10 mg	1	0	0	2
RTA 901 80 mg	0	1	2	0

The label on each bottle will contain, at minimum, the following information:

- Medication ID number;
- Protocol 901-C-2102;
- Expiry date;
- Contains 30 capsules;
- Study Drug Caution: New Drug Limited by Federal (or United States) Law to Investigational Use. Keep out of reach of children;
- Control or lot number;
- Store at 15°C to 25°C (59°F to 77°F);
- Reata Pharmaceuticals, Inc., Plano, TX 75024

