## 7.6. Treatment Compliance

The Investigator or his/her designated and qualified representatives will only dispense study drug to subjects enrolled in the study in accordance with the protocol. Subjects should administer study drug exactly as instructed by the site. Non-compliance is defined as taking less than 80% or more than 120% of expected study drug during any evaluation period (visit to visit).

Subjects should record in the e-diary all administered and missed doses of study drug. The reason for a missed dose should be recorded in the e-diary. A missed dose includes drug holidays and temporary study drug discontinuations. Subjects will be asked to return all unused study drug (study drug bottles and any unused capsules).

Refer to Section 5.1.7 for compliance related to PRO completion via the e-diary.

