3.6. Analysis Sets

Intent-to-Treat Analysis Set (ITT)

The ITT analysis set is defined as all randomized subjects who receive at least 1 dose of randomized study drug. The ITT analysis population will be used for the primary, secondary and exploratory efficacy endpoints. In analyses performed on the ITT analysis set, participants will be analyzed according to their planned treatment group.

Per-protocol set

The per-protocol population will include the ITT subjects who do not have any major protocol deviations deemed to meaningfully impact efficacy assessments. Subjects will be analyzed by randomized treatment.

Major protocol deviations that could impact efficacy include the following, although further efficacy-related deviations may be identified prior to treatment unblinding at database lock:

 Failing/meeting at least one relevant inclusion/exclusion criterion that could impact efficacy

• <80% or >120% treatment compliance during DB period based on time on treatment

• Prohibited medication use that could impact efficacy

Using of rescue medication over the prespecified daily limits during Run-in and treatment period:

- Acetaminophen/paracetamol not to exceed 3000 mg per day;
- Ibuprofen not to exceed 1200 mg per day (protocol version 3.0);
- Ibuprofen not to exceed 600 mg per day (protocol version 4.0).

A per-protocol analysis of the primary endpoint will be performed.

Safety Analysis Set

The safety analysis set includes all randomized subjects who receive at least 1 dose of randomized study drug. The safety analysis set will be used for evaluation of safety variables. In analyses performed on the safety analysis set, participants will be analyzed according to their actual treatment received. Subjects who receive at least 1 dose of RTA 901 will be classified in the RTA 901 group.

4. List of Planned Study Analyses

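### The full-kit credit for an unreturned kit in SAP 5.6 can hide heavy under-dosing, and can score an adherent subject above 120% when a kit is lost early and replaced

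*SAP*

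**What the plan says.** SAP 5.6 computes compliance from the capsules dispensed and returned on the eCRF: doses dispensed minus doses returned, divided by the "total number of exposure days of the randomized study drug". A kit that does not come back has no count, so the SAP assigns a value by one of two rules:

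- If the subject "had a subsequent dispensation, then the non-returned kit is assumed to have been taken in full".
- But "if a kit is not returned and no kit is subsequently dispensed, then the non-returned kit is assumed to not have been taken".

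A full kit is 30 doses. Protocol 7.3 says that in Part 1 "each bottle of study drug will contain 30 capsules of 10 mg or 40 mg strength RTA 901" or matching placebo, and SAP 5.6 says "One dose requires a capsule from 3 bottles". SAP 5.6 has no cap at the days until the next dispensation, no reference to the e-diary, and no exception for a lost kit.

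The trial does hold a dose-level record. Protocol 7.6 states "Subjects should record in the e-diary all administered and missed doses of study drug", and Protocol 7.5 and SAP 3.2 also place each dose in the e-diary.

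The result has a use beyond description. SAP 3.6 lists "<80% or >120% treatment compliance during DB period based on time on treatment" among the major deviations for the per-protocol set, and SAP 6.3 repeats the primary MMRM on that set as a sensitivity analysis.

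**The concern.** The rule fixes a value that the trial measures, and the fixed value does not depend on what the subject took. It can go wrong in two directions.

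- **Under-dosing hidden.** A subject who skipped most of an interval and did not return that kit is scored as if every capsule had been swallowed.
- **Adherence scored as excess.** Protocol 5.6 allows unscheduled dispensing: study drug dispensation is the first item under "Unscheduled visits conducted for the following reasons do not require additional assessments unless deemed necessary by the Investigator". A replacement kit is a later dispensation, so the lost kit earns 30 doses on top of those used from the replacement.

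The first error can keep a subject below 80% in the per-protocol set. The second can put a fully adherent subject over the upper limit. Both distort the compliance table.

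**Working it through.** The documents report no compliance figure to reproduce, so the check applies the SAP 5.6 formula to typical records.

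**Inputs**
- Dispensing of randomized drug at Day 1, Week 4 and Week 8 (schedule of assessments in both documents). Assumed: one 30-dose kit each time, nominal 28-day intervals.
- Exposure days D = last dose − first dose + 1 (SAP 5.5): 84, or 85 if a dose is taken on Day 85.
- Assumed: all other kits are returned and counted correctly.

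**Ordinary unreturned earlier kit, no dose missed.** The credit is 30 where 28 were taken, so the score is (D + 2)/D.
- D = 84: 86/84 = 102.4%. Two such kits: 88/84 = 104.8%.
- D = 85: 87/85 = 102.4%. Two such kits: 89/85 = 104.7%.
- Neither limit is crossed.

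**Missed doses in an interval whose kit is unreturned.** With m doses missed there and none elsewhere, true compliance is (D − m)/D. The SAP score stays at (D + 2)/D for every m.

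| D | m | True | SAP score |
|---|---|---|---|
| 84 | 17 | 67/84 = 79.8% | 102.4% |
| 84 | 28 (whole second interval) | 56/84 = 66.7% | 102.4% |
| 85 | 17 | 68/85 = 80.0% | 102.4% |
| 85 | 18 | 67/85 = 78.8% | 102.4% |
| 85 | 20 | 65/85 = 76.5% | 102.4% |

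The true value falls below 80% from m = 17 (D = 84) or m = 18 (D = 85).

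**Kit lost after x doses, replaced at once, no dose missed.** The lost kit is credited with 30 and the other D − x doses are counted correctly, so the score is (30 + D − x)/D. The true value is 100%.

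| x | D = 84 | D = 85 |
|---|---|---|
| 0 | 114/84 = 135.7% | 115/85 = 135.3% |
| 7 | 107/84 = 127.4% | 108/85 = 127.1% |
| 12 | 102/84 = 121.4% | 103/85 = 121.2% |
| 13 | 101/84 = 120.2% | 102/85 = 120.0% |
| 14 | 100/84 = 119.0% | 101/85 = 118.8% |
| 28 | 86/84 = 102.4% | 87/85 = 102.4% |

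The score exceeds 120% only for x up to 13 (D = 84) or 12 (D = 85). Even at x = 0 it stays above 120% only if no more than 13 (D = 84) or 12 (D = 85) doses were missed elsewhere. Shorter exposure widens the range: x up to 18 at D = 56 (68/56 = 121.4%) and up to 24 at D = 28 (34/28 = 121.4%).

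**The last-kit rule, for comparison.** A fully adherent subject who fails to return only the last kit scores 56/84 = 66.7%.

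**Frequency.** The documents give no rate of unreturned or replaced kits. At an assumed 2% to 5% of subjects, 64 × 0.02 = 1.3 to 64 × 0.05 = 3.2 per arm would have a kit scored by this rule. Only some of them would cross a limit.

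**The case against.** The strongest reply is that the rule is close to right in routine use and that other provisions would catch the extreme cases.

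- In scheduled intervals the 30-dose credit is near the doses due, and an adherent subject with one or two unreturned kits scores 102% to 105%. This stands.
- Hidden under-dosing needs 17 or 18 missed doses in one interval and that same kit unreturned. Protocol 7.6 judges compliance visit to visit, Protocol 4.6.2 calls for an evaluation after three consecutive missed days, SAP 5.4 keeps a deviation log, and SAP 3.6 leaves room for further efficacy deviations to be identified before unblinding. Such a subject may well be found. This stands in part: these routes rely on judgement, and the stated criterion still gives the wrong value.
- Protocol 5.6 does not mention lost kits, and the documents do not show how a lost kit is entered on the return form. So the replacement case is an inference, though a natural one. The option to add deviations does not help here. Only the general wording of SAP 3.6, that a deviation must matter for efficacy, could keep the subject in.
- Self-reported dosing is not plainly better than a capsule count. That is true, but for an unreturned kit there is no count.

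A reader might infer that any lost-and-replaced kit exceeds 120%. The arithmetic does not support this: losses after the first 12 to 13 doses stay at or below the limit over a full 12 weeks. A reader might also infer that recorded missed doses are lost to the trial. They drop out of this one percentage and remain in the e-diary.

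**Conclusion.** The point holds as a conditional one. For an unreturned kit followed by another dispensation, the SAP 5.6 score is unrelated to the doses taken, and it feeds a stated per-protocol criterion. Over a full 12 weeks it can score a subject who is truly below 80% at about 102%, and it can put an adherent subject above 120% if a kit is lost within about its first 12 to 13 doses and replaced. These figures assume one 30-dose kit per scheduled dispensation, nominal visits and correct counts for the other kits.

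The consequence is limited to the compliance summary and the per-protocol sensitivity analysis. It would be wrong to read this as a threat to the primary result: the ITT MMRM and the testing sequence of 80 mg then 10 mg do not use compliance. Nor do the documents show that any subject will be misclassified. The number is unknown and probably small. This is a minor correction, worth making because it is cheap.

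**What to change.** In SAP 5.6, replace the full-kit credit with a rule along these lines:

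- For a kit not returned but followed by another dispensation, doses taken are those recorded as taken in the e-diary from its dispensation to the next one, capped at the smaller of the days in that interval and 30.
- Where dosing entries are missing for some days, those days count as taken unless a missed dose or an interruption is recorded, under the same cap.
- This value is used for the 80%/120% per-protocol criterion.

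Revise the zero-dose rule for an unreturned last kit in the same edit. The text should also reconcile the whole-period measure in the SAP with the visit-to-visit definition in Protocol 7.6.

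With complete diaries, the subject with 17 missed doses scores 67/84 = 79.8%, and the adherent subject with a replaced kit scores 84/84 = 100%.

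The cost is a short change to one SAP paragraph and a merge with dosing data already collected, settled before unblinding. Diary dosing is self-reported, and counting blank days as taken is still generous. Both apply only where no capsule count exists, and the cap limits the error to the days in the interval.

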5.7. Prior and Concomitant Treatments and procedure

5.7.1. Standard of Care Pain Medications

Subjects are required to take only 1 SOC pain medication for neuropathic pain (consistent with regional or local SOC guidelines for DPNP) at a stable dose (defined as < 50% change in total dose) that does not exceed the maximum dose in the prescribing information for approximately 4 weeks prior to Screening. Allowed SOC pain medications include duloxetine, pregabalin, and gabapentin. Attempts should be made to maintain the stable dose of pain therapy. If changes to the dose are necessary, the Investigator should discuss with the Medical Monitor. However, dose level should not be above the maximum prescribed dose as instructed in the medication's dosage and administration section of the prescribing information.

5.7.2. Allowed Medications

The following medications and therapeutics are allowed during the study:

 Benzodiazepine, zolpidem, diphenhydramine, or related drugs for insomnia if the subject is on a stable dose for 3 months prior to entry and it is not anticipated to change during the study;

 SSRI (selective serotonin reuptake inhibitor) for depression if the subject is on a stable dose for 3 months prior to entry and it is not anticipated to change during the study;

- NSAIDs prescribed for conditions other than DPNP.
- Aspirin ≤325 mg/day for cardiac prophylaxis.
- Rescue medication, see Section 7.8.3.

5.7.3. Rescue Medication

Rescue medication for DPNP is in addition to standard of care medication (gabapentin, pregabalin or duloxetine) for DPNP. Rescue medication is intended to treat temporary elevations in a subject's DPNP and is intended to be used occasionally and not meant to be used for prolonged periods of time.

Prior to implementation of protocol 4.0, if rescue medication is needed, subjects will be instructed to take acetaminophen 500 mg every 4 to 6 hours as needed (not to exceed 3000 mg per day) or ibuprofen 200 to 400 mg every 4 to 6 hours as needed (not to exceed 1200 mg per day) (protocol version 3.0).

Subjects who enter screening after implementation of protocol Version 4.0 may only use acetaminophen as a rescue medication for DPNP as needed. If rescue medication is needed for DPNP, subjects will be instructed to take acetaminophen 500 mg every 4 to 6 hours as needed (not to exceed 3000 mg per day).

Subjects currently in the study at the time of implementation of protocol Version 4.0 using ibuprofen as rescue medication for DPNP may switch their rescue medication to acetaminophen (i.e., no longer use ibuprofen as a rescue medication for DPNP) or continue to use as rescue medication for DPNP ibuprofen 200 to 400 mg every 4 to 6 hours as needed (not to exceed 600 mg/day) for up to 3 days in a 7-day period (not calendar week). Subjects unable to comply with these conditions will need to discontinue study treatment and withdraw from the study; some or all of such subjects may be replaced at the discretion of the Sponsor. The daily maximum dosages stated in this section are inclusive of those used outside of treatment for DPNP. Any questions related to rescue medications should be directed to the Medical Monitor prior to administration when possible.

5.7.4. Prohibited Medications

The following medications and therapeutics are prohibited during the study:

- Neuroleptics, monoamine oxidase inhibitors, N-methyl-D-aspartate receptor ligand for pain (ketamine, amantadine, dextromethorphan [except low dose intermittent use for cough], memantine, methadone, dextropropoxyphene, and/or ketobemidone), and/or alpha-lipoic acid;
- Tricyclic antidepressants and other tricyclic drugs including cyclobenzaprine and promethazine; triptans (prescribed usage outside of DPNP allowed); and/or 5-HT3 receptor antagonists;

• Drugs or chemicals that may cause neuropathy and interfere with clinical evaluation. Agents include but are not limited to pyridoxine, hydralazine, metronidazole, phenytoin, dapsone, amiodarone, nitrofurantoin, paclitaxel, vinblastine, vincristine, cisplatin, etoposide, didanosine, disulfiram, suramin, zalcitabine, anti-tuberculosis medications (eg, isoniazid, rifampin, ethambutol, ethionamide), heavy metals, and industrial solvents;

- Strong or moderate CYP3A4 inhibitors or inducers and P-gp inhibitors;
- Topical pain medications intended to treat pain associated with DPNP (including but not limited to lidocaine 5% patch, over-the-counter capsaicin, amitriptyline, and/or isosorbide dinitrate spray);
- Prescription patch containing 8% capsaicin;
- Opioid or opioid based drugs;
- Central nervous system active drugs such as cocaine, amphetamines, and cannabinoids (marijuana);
- Oral prednisolone or equivalent are excluded during the Screening and Run-in Periods;
- NSAIDs for DPNP (applies only to subjects who enter the study following implementation of protocol Version 4.0) (see Section 5.7.2 of the protocol for NSAIDs prescribed for conditions other than DPNP);
- Muscle relaxers.

5.7.5. Prohibited Devices/Procedures

- TENS unit for the treatment of DPNP;
- Implantation of neurostimulators;
- Nerve decompression surgery for treatment of DPNP;
- Steroid or local anesthetic nerve blocks:
- Cryotherapy, intrathecal/epidural opioids, or botulinum toxin;
- Alternative medicine products or treatments (eg, acupuncture, naturopathy, homeopathy, etc.).

Concomitant medications/procedure include those being taken at Screening or at any point throughout the study, up to and including the Week 16/EOS visit. Concomitant medication/procedure will be recorded on eCRFs by their trade and/or generic name and will include dose and duration of treatment. Subjects requiring excluded medications will not be eligible for the study. Planned deviations from the eligibility criteria, with regard to excluded medications, will not be approved. Subjects will be instructed to consult with the Investigator or

Product: RTA 901 (BIIB143) Statistical Analysis Plan Study: 901-C-2102 Version: 1.0

other site personnel before taking any newly prescribed medications, over-the-counter medications, or supplements/herbal preparations. If a subject requires use of a prohibited medication during the study, the Medical Monitor should be contacted to determine whether an alternative drug is feasible and if not, how to handle dosing with study drug while the prohibited medication is being used. Documentation of these discussions must be maintained in the subject's source records.

All concomitant medications will be coded using the World Health Organization drug dictionary (WHO Drug).

All concomitant non-drug treatments/procedures will be coded using the Medical Dictionary for Regulatory Activities (MedDRA V24 or higher).

For the purposes of analysis concomitant medication (including medication or procedure) is defined as any therapy that was taken or administered on or after first randomized dose including follow-up period up to Week 16 (EOS). This includes therapies and procedures that were started prior to first randomized dose, if their use continued on or after the first randomized dose

Medications/therapies with missing start or stop dates, will also be considered as concomitant during double-blinded period as criteria below:

- If both the start and stop dates of a medication/treatment/procedure are missing.
- If the start date of a medication/treatment/procedure is missing and the stop date of the medication/therapy occurred on or after the date of first randomized dose of study drug.
- If the start date of a medication/treatment/procedure therapy occurred prior to the date of
 first randomized dose of study drug and the stop date of the
 medication/treatment/procedure is missing and the medication/treatment/procedure is
 listed as ongoing.
- If the start date of a medication/treatment/procedure occurred prior to the date of first
 randomized dose of study drug and the stop date of the medication/treatment/procedure is
 missing and the medication/therapy is not listed as ongoing, then the
 medication/treatment/procedure will be considered as concomitant.

The number and percentage of participants taking any concomitant medications will be summarized (including categories: prohibited medications, standard of care, allowed medications, and rescue medications) for the safety analysis population during double blinded period by treatment group and overall. The number and percentage of participants taking any concomitant non-drug treatments will also be summarized for the safety analysis population by treatment group and overall.

Prior medication (including medication or procedure) used during the run-in period is defined as any therapy that was taken or administered on or after the start of the run-in period to prior to the first randomized dose. This includes therapies and procedures that were started prior the start of the run-in period, if their use continued on or after the start of the run-in period.

The number and percentage of participants taking any prior medication during run-in period (before randomized treatment start date) will also be summarized for safety population by treatment and overall.

Concomitant medications will also be reviewed by a medical reviewer prior to the lock to determine allowed, prohibited medications and procedures according to the protocol. These will be summarized separately.

6. Efficacy endpoints

